5.10. List of variables

Variables	Type	Value	Expression
Clinical			
Age	Discrete	In completed years	Mean±SD
Sex	Categorical	Male/Female	Frequency (%)
Duration of HD	Discrete	In completed years	Mean±SD
Duration of pruritus	Discrete	In completed months	Mean±SD
Cause of CKD	Categorical	GN/HTN/DM	Frequency (%)
Baseline use of antipruritic medication	Categorical	Absent/Present	Frequency (%)
WI-NRS score	Discrete	0-10	Mean±SD
Skindex-10 scale total score	Discrete	0-60	Mean±SD
Biochemical			
Calcium	Continuous	mmol/l	Mean±SD
Phosphate	Continuous	mmol/l	Mean±SD
PTH	Continuous	pg/ml	Mean±SD

Operational definitions:

- **Chronic Kidney Disease-Associated Pruritus:** CKD-aPis defined as severe and persistent itching directly related to kidney disease, without other underlying skin or systemic causes to explain the itching. (Hector alve..et al 2020)
- **MHD:** Maintenance haemodialysis was defined as regular haemodialysis treatment for at least 3 months for the management of ESKD.(Mambap, A.T., Che, I.A., Mahamat, M. *et al.* 2022)
- **Skindex-10:** The Skindex-10 scale was developed specifically for uremic pruritus and measures the weekly effect of itch across three domains (disease, mood and emotional distress, and social functioning) Scores on the Skindex-10 scale range from 0 to 60, with higher scores indicating worse itch-related quality of life. (Mathur et al., 2010).
- **Moderate-to-severe pruritus** will be defined as a mean score of >4 points on the 24-hour WI-NRS score calculated.Itching severity scores have been categorized in the literature as mild (<4), moderate (≥ 4 to <7), or severe (≥ 7) (Reich et al., 2012).
- **Efficacy outcomes:** The primary efficacy outcome will be the percentage of patients who will have an improvement (decrease) of at least 3 points from baseline at week 6 in the weekly mean score on the daily WI-NRS (Fishbane et al., 2020). The prespecified secondary efficacy outcomes will be the mean change from baseline at week 6 in the Skindex-10 scale total score (Fishbane et al., 2020).
- **Standard Symptomatic Treatment for Itching:** Standard Symptomatic treatment using antihistamin is useful. Gabapentin or Pregabalin UVB therapy ,oral charcoal or nalfuralfine might be the next line of therapy.(Mettang and kremer 2014)

5.11. Data collection instrument: A structured pretested case record form.

5.12. Data collection procedure:

Baseline assessment: CKD patients in HD will be screened consecutively and prospectively by the above inclusion and exclusion criteria to select eligible patients. Eligible patients and their legal relatives will then fully explain the study protocol, their role in the study, and the risks of the study. They will be informed of their right to withdraw from the study at any stage. After getting written informed consent, they will be finally enrolled in the study. Detailed history clinical examination and relevant investigation will be done. Baseline demographic, clinical and biochemical information will be collected from the patients using the case record form and the scales. Blood samples will be collected after an overnight fasting period, with all aseptic precaution 5 mL of venous blood drawn into appropriate vacutainers. iPTH will be measured using a chemiluminescence immunoassay (CLIA). Serum calcium and phosphate will be analyzed using colorimetric methods on a Beckman Coulter AU480 or equivalent validated clinical chemistry analyzer.

Allocation: Once a participant is enrolled in the study and consents to participate, they will be assigned to a treatment group according to the randomization sequence. This assignment will be done immediately after the baseline assessment to ensure that it is truly random. Patients will be randomly assigned to either experimental group or placebo group with a 1:1 allocation. Randomization will be carried out using online software (Research Randomizer Version 4.0 at <https://www.randomizer.org>).

Blinding: The study will be conducted as a double-blind trial, meaning that both the participants and the investigators will be unaware of the treatment assignments.

Interventions:

In the experimental group:

Standard symptomatic treatment for itching + Difelikefalin Dose : 0.5 µg per kilogram of weight after each dialysis session.

Duration: 6 wks

In the control group:

Standard symptomatic treatment for itching + Placebo

Duration: 6 wks

Follow-up:

- i. At the end 3 wks by- WI-NRS scale, Skindex 10 scale & Adverse events
- ii. At the End of 6 wks: WI-NRS scale, Skindex 10 scale & Adverse events

During the 6-week intervention period, patients will report their worst itching intensity using the WI-NRS, and their quality of life will be assessed using the Skindex-10 questionnaire at prespecified follow-up intervals throughout the 6-week period.

Safety will be evaluated by monitoring adverse events, vital signs, clinical laboratory measurements in both group.

5.13. Data analysis:

Data will be entered into an Excel sheet to generate the master sheet. After completion of data collection, master sheet will be fed into SPSS (Windows version 27.0) for analysis. This study has two types of data: Categorical and quantitative data. Kolmogorov–Smirnov (K-S) test will be used to determine the data distribution. Finding if there is a significant difference between the data, independent samples t-test (or Mann–Whitney test in case of non-parametric data) and Chi-square test for continuous and categorical data, respectively will be used. The difference between the repeated variable in distinct visits using repeated ANOVA with the change from baseline in the weekly mean WI-NRS scale, Skindex 10 Scale. The adjusted mean difference between the groups and its two-sided 95% CI will be presented. A p -value < 0.05 will be considered significance.

5.14. Expected outcomes: Difelikefalin will significantly reduce pruritus severity compared to placebo. Participants receiving difelikefalin will report improvements in quality of life and will exhibit a favorable safety profile, with no major adverse events.

5.15. The utilization of results: This trial will provide critical evidence on the effectiveness and safety of difelikefalin in a resource-limited setting, addressing a significant unmet need in the management of CKD-aP. If proven effective, difelikefalin could become a standard treatment option for CKDaP and improve the quality of life for hemodialysis patients in Bangladesh and similar populations globally. Efforts will also be made to present these results at conferences and publish them in peer-reviewed national and international journals. The results and observations of the study will be published as a thesis and submitted to the respective university as a part of the requirement for the MD (Nephrology) Phase B examination purpose. The results of the study will be presented to the Department of Nephrology, CMCH.

[figure not shown]
5.16. Ethical implication: Voluntary written consent will be taken from the patient/and legal guardians. All measures will be taken to protect anonymity. The interviews of the patient, clinical examination and investigations will be performed at the respective hospital after explaining the nature and purpose of the study to them, assuring that the information given by them will be used for the interest of the community and that the particulars of the patients will not be disclosed anyway. An independent safety monitoring committee conducted unblinded monitoring of patient safety throughout the trial. The trial protocol will be approved by the Ethical Review Committee of Chittagong Medical College.

Schedule:

Time Schedule (GANTT CHART)

	1 st	2 nd	3 rd	4 th	5 th -6 th	7 th -18 th	19 th - 21 th	22 th - 23 th	24 th
Problem definition									
Literature review									
Research design									
IRB clearance									
Data collection									
Data analysis									
Report writing									
Submission									

5.17 Study flow chart:

5.18 References:

- Brennan, F., 2024. The Pathogenesis of CKD–Associated Pruritus (CKD-aP): A Theoretical Model and Relevance for Treatment. *Kidney360*, pp.10-34067.
- Brennan F. Emerging insights into the mechanisms of CKD-associated pruritus. *JNephrol Res*. 2024;12(1):15–22.

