Degree	Institute	University/Board	Field	Year
M.B.B.S			Passed	

3. Field of study : Nephrology
4. Research experience : None
5. Percentage of time to be devoted to this project : 100%
6. Number of Scientific Publication : None

.....

Signature of the Student

PART-C

Summary

Background: Pruritus is a common and distressing symptom among hemodialysis patients with chronic kidney disease (CKD), significantly impacting their quality of life. Difelikefalin, a selective kappa-opioid receptor agonist, has shown promise in alleviating CKD associated pruritus (CKDaP). However, its efficacy and safety in the Bangladeshi population remain under-explored. **Objectives:** This study aims to evaluate the effect of Difelikefalin, compared to placebo, in reducing pruritus, improving quality of life in CKD patients on maintenance hemodialysis. **Materials and Methods:** A randomized, placebo-controlled trial, double-blinded, will be conducted in the Department of Nephrology of Chittagong Medical College Hospital, Chattogram, Bangladesh for one and half years. A total of one hundred two CKD patients on maintenance hemodialysis will be included in this study. Patient with moderate-to-severe pruritus (Worst Itching Intensity Numerical Rating Scale [WI-NRS] score ≥ 4) will be enrolled and randomly assigned in a 1:1 ratio to receive either Difelikefalin (0.5 mcg/kg) or a placebo intravenously after each hemodialysis for 6 weeks. The primary outcome measure will be the change in WI-NRS score from baseline to week 6. Secondary outcomes will be measured by Skindex 10 scale. Adverse events and safety measures will also be recorded. The primary analysis will follow either an intention-to-treat or a per-protocol approach and will be performed using SPSS version 27. **Discussion:** Data from previous studies indicate that Difelikefalin can reduce the severity of itching and improve the quality of life in CKD patients on maintenance hemodialysis. Clinical trials are needed to better understand the safety and efficacy of Difelikefalin in CKD patients in our population.

PART-D

1. Introduction:

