- What is the effect of difelikefalin on CKD-associated pruritus in patients on maintenance hemodialysis?

3.2 Research hypothesis:

- Difelikefalin effectively reduces CKD–associated pruritus in maintenance hemodialysis patients.

4. Objectives

4.1 General objective:

- To evaluate the effect of difelikefalin in CKD-associated pruritus on maintenance hemodialysis patients.

4.2 Specific objectives:

- I. To determine the baseline scores of the WINRS scale and Skindex-10 scale in CKD-associated pruritus on maintenance hemodialysis patients..
- II. To estimate and compare the changes in the WINRS scale, and Skindex-10 Scale between the experimental and control groups.
- III. To assess the tolerability and detect any adverse effect of Difelikefalin in patients with CKD-associated pruritus on maintenance hemodialysis throughout the study period.

5. Materials and method:

5.1. Type of study: Randomized, placebo-controlled, double-blinded trial,

5.2 Place of Study: Department of Nephrology, Chittagong Medical College Hospital, Chattogram, Bangladesh.

5.3 Study period: One and half years from acceptance of protocol.

5.4 Study population: Adult CKD stage-5 patients on MHD in the dialysis unit of the Department of Nephrology, CMCH during the study period.

5.5 Study groups: Based on the interventions, there will be two groups in the study

I. Experimental group:

Standard symptomatic treatment for itching + Intravenous difelikefalin

II. Control group:

Standard symptomatic treatment for itching + Placebo

5.6 Sampling technique: Consecutive sampling. From the Selected participants, the intervention and control will be randomly assigned in a 1:1 ratio (block size of four) through computer-generated randomization.

5.7. Inclusion criteria:

- i. Adults aged ≥ 18 years.
- ii. Patient with chronic kidney disease on HD for ≥ 3 months.
- iii. Moderate-to-severe pruritus (WI-NRS score ≥ 4).
- iv. Able to communicate clearly with the Investigator .
- v. Willing and able to provide written informed consent prior to participating in this study.

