5.8 Exclusion criteria

- i. Known case of Primary skin disease associated with Itching.
- ii. Known case of liver disease.
- iii. Known case of iron deficiency anaemia ,hematological malignancy.
- iv. Known case of hypothyroidism & hyperthyroidism.
- v. Known case of allergic reaction to Opiates .
- vi. Pregnancy.
- vii. Drug abuse, or substance dependence.

5.9. Sample size: Sample size calculation for hypothesis testing of difference between two proportions:

$$n = \frac{p(100 - p) + q(100 - q)}{(p - q)^2} (z_{\alpha} + z_{\beta})^2$$

Where,

Z_{α} = Z value of standard normal distribution at a definite level of significance

Z_{β} = Z value of standard normal distribution at a definite level of power

p = Proportion of patients with expected outcome (response rate) in the experimental group

q = Proportion of patients with expected outcome (response rate) in the control group

Here,

Z_{α} = 1.96 at 95% Confidence Interval

Z_{β} = 1.63 at 95 % power

p = 64% (Fishbane et al., 2020b)

q = 29% (Fishbane et al., 2020b)

So,

$$n = \frac{64(100.0 - 64) + 29(100.0 - 29)}{(64 - 29)^2} (1.96 + 1.63)^2 \approx 46$$

Considering 10% lost to follow-up final sample will be

$$(46 + 46 \times 10\%) \approx 50.6 \approx 51$$

That means 51 patients in each group will be needed in each group to test the hypothesis.

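### Section 5.10 makes a 3-point responder cut of WI-NRS the primary outcome, although the Summary, objective II and 5.13 use the full 0-10 change; the cut probably costs power, by an amount that depends on how the scores are distributed

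*Protocol*

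**What the plan says.** Under the operational definitions in 5.10 the "primary efficacy outcome will be the percentage of patients who will have an improvement (decrease) of at least 3 points from baseline", assessed at week 6, with an earlier difelikefalin trial cited for the definition. No reason is given for preferring the cut to the score itself.

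Section 5.9 follows the same form: "Sample size calculation for hypothesis testing of difference between two proportions", with response rates of 64% (experimental) and 29% (control), "1.96 at 95% Confidence Interval" and "1.63 at 95 % power". It arrives at 46 per group, raised to 51 for 10% loss. Section 5.9 does not define response; I read it as the 3-point fall of 5.10.

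Elsewhere the full scale is used:

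- Part C, Summary: "The primary outcome measure will be the change in WI-NRS score from baseline to week 6".
- Section 4.2, specific objective II: compare changes in WI-NRS and Skindex-10 between the groups.
- Section 5.10, variable list: WI-NRS as a 0-10 score summarised by mean and SD.
- Section 5.13: after the general rule ("Chi-square test for continuous and categorical data, respectively will be used"), a repeated ANOVA on the change from baseline in weekly mean WI-NRS, with an adjusted mean difference and two-sided 95% CI. It is the only analysis in 5.13 that names WI-NRS.
- Case record form: the score itself at baseline, week 3 and week 6.

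**The concern.** Reducing an 11-level score to yes/no usually loses power, and here the score is already collected and already planned for analysis. What is at stake is how well the trial withstands a benefit smaller than the one taken from a single cited trial.

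The cut also treats patients unevenly. Entry requires WI-NRS of at least 4. A patient entering at 4 must reach 1 or less (3/4 = 75% reduction), while one entering at 10 need only reach 7 (3/10 = 30%). A 2-point fall counts the same as no change or worsening.

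The Summary and 5.10 name different primary outcomes, so one of them has to be changed in any case. The power comparison is a reason for choosing between them.

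**Working it through.** **Inputs from the protocol.** Response 64% and 29%, z values 1.96 and 1.63, 10% loss, 51 per group (all 5.9); 1:1 allocation (5.6); p-"value < 0.05 will be considered significance" (5.13). Of 51 enrolled, 10% loss leaves about 46.

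**The plan's own figure.** [0.64 × 0.36 + 0.29 × 0.71] / 0.35² × (1.96 + 1.63)² = 0.4363 / 0.1225 × 12.888 = 45.9, so 46. Then 46 × 1.10 = 50.6, so 51. The stated figures reproduce.

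**Added assumption.** The protocol gives no SD, mean change or distribution for WI-NRS. To compare the two forms of outcome I assume that the change is normal with the same SD in both arms. The two rates then imply a standardised difference d = z(0.64) − z(0.29) = 0.358 + 0.553 = 0.912.

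**Power at 46 per arm, two-sided 5%.** Responder test: exact binomial enumeration of the Pearson chi-square. Full-scale change: noncentral t, 90 degrees of freedom, noncentrality d × √(46/2).

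| Effect | d | Noncentrality | Responder | Full scale | Gain (points) |
|---|---|---|---|---|---|
| 64% vs 29% | 0.912 | 4.37 | 92.8% | 99.1% | 6.3 |
| 55.25% vs 29% | 0.685 | 3.29 | 72.1% | 90.2% | 18.1 |

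The second row takes three-quarters of the difference: 29 + 0.75 × 35 = 55.25. With a continuity correction the responder test has 89.4% and 64.7%. If all 51 per arm are evaluable, the gains are 99.5 − 96.0 = about 3.6 and 92.9 − 79.2 = about 13.7 points. Under the normal model the responder test needs 72 per arm to match the t-test at 46, a relative efficiency of 46/72 = 64%.

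**Sensitivity to the added assumption, 46 per arm.** In the shift models the shift in score, rather than the response difference, is cut by a quarter. The gain is full-scale power minus responder power.

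| Model | Gain, full effect | Gain, three-quarters effect |
|---|---|---|
| Normal, treated SD 0.8 × control | 99.4 − 93.3 = 6 | 91.6 − 68.1 = 24 |
| Normal, treated SD 1.5 × control | 98.4 − 93.3 = 5 | 86.8 − 78.4 = 8 |
| Logistic shift, t-test | 4 | 11 |
| Logistic shift, Mann–Whitney | 5 | 14 |
| Heavy tails (t, 4 df), t-test | −1 | 0 |
| Heavy tails (t, 4 df), Mann–Whitney | 4 | 12 |
| Responder/non-responder mixtures, t-test | about −3 to +6 | about −5 to +12 |

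The unequal-SD rows use a normal approximation; the logistic, heavy-tail and mixture rows are simulated. The mixtures assume mean falls of 4 to 5 points in responders and 0 to 1 in the others, with SD 1 to 2, calibrated to the stated rates. These settings are assumptions, and others would move the limits somewhat.

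**The case against.** The strongest reply is that the responder outcome is clinically readable, follows the cited trial and has about 93% power at the assumed effect. It adds that 5.13 already plans the full-scale analysis with a mean difference and CI, and that resolving the conflict in favour of the Summary removes the loss. All of this stands. It limits the point to which outcome should be primary and how much robustness that choice buys.

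A reader might infer more than the documents support:

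- *That the loss follows from the plan's own assumptions.* The plan supplies rates, error level and sample size only. The normal equal-SD shift is added here, and the gain can vanish or reverse. The Introduction reports that about 20% of patients had no clinically meaningful reduction in itch, so a responder/non-responder split is worth considering.
- *That most of the information is discarded.* Under the normal model the efficiency is 64%, so about 36% is lost.
- *That the risk of a missed effect is several times larger than necessary.* The contrast of 7.2% with 0.9% holds only under the normal model at full effect.
- *That a smaller effect is to be expected because both arms receive standard antipruritic treatment.* The protocol does not say whether the cited trial allowed background treatment, so this cannot be argued from the document. The smaller effect is a robustness case, not a forecast.

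**Conclusion.** The point holds in a limited form. Sections 5.9 and 5.10 build the primary outcome on a cut score, while the rest of the protocol works with the full scale. Under a normal equal-SD shift, moving to the full scale raises power from about 93% to about 99% at the assumed effect, and from about 72% to about 90% if the response difference is a quarter smaller. At that smaller effect the gain is roughly 8 to 24 points across unequal-SD and logistic shift models, and roughly -5 to +12 points under a clear responder/non-responder split. The trial is not underpowered at its stated effect. The material benefit is protection against a smaller one, and it is likely rather than certain. The loss applies only if 5.9 and 5.10 govern over the Summary.

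**What to change.** - **5.10:** make the change in WI-NRS from baseline to week 6, on the full 0-10 scale, the single primary efficacy outcome, matching the Summary. Make the proportion with a fall of at least 3 points the first secondary outcome.
- **5.13:** name the between-group mean difference with 95% CI, which is already planned, as the primary result. Report the responder proportion as a risk difference with 95% CI.
- **5.9:** keep 51 per group. State the power of the full-scale comparison only together with its distributional assumption and a range, since the protocol gives no SD.

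The cost is wording, provided the changes are made before data are seen; no patients, visits or measurements are added. There are two small downsides. The primary result is no longer directly the responder rate of the cited trial, though that rate stays available as first secondary. And if patients do split sharply into responders and non-responders, the full-scale test could be slightly the weaker of the two.

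### Standard itch treatment belongs to both 6-week regimens, but patients on no antipruritic may enter; randomisation is not stratified on this, and the protocol does not say whether the treatment is continued or newly started

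*Protocol*

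**What the plan says.** Protocol 5.5 introduces the arms with "Based on the interventions, there will be two groups in the study" and lists standard symptomatic treatment in each. Section 5.12 (Interventions) repeats this with a 6-week duration: "Standard symptomatic treatment for itching + Difelikefalin Dose" in one arm and "Standard symptomatic treatment for itching + Placebo" in the other. The operational definition in 5.10 is loose. It says "Standard Symptomatic treatment using antihistamin is useful" and names several possible next-line options, but does not say when treatment starts or whether it must be stable.

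The 5.10 variable list includes "Baseline use of antipruritic medication" with the values Absent and Present, and the case record form has a field for it. The itch entry criterion in 5.7 is "Moderate-to-severe pruritus (WI-NRS score ≥ 4" or more. Nothing in 5.7 or 5.8 asks for prior or stable antipruritic use.

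On allocation, 5.12 states: "This assignment will be done immediately after the baseline assessment to ensure that it is truly random". Section 5.6 has patients "randomly assigned in a 1:1 ratio (block size of four) through computer-generated randomization", and neither section names a stratification factor. The 5.10 primary outcome is a fall of at least 3 points in weekly mean WI-NRS from baseline to week 6. Section 5.13 promises an adjusted mean difference without naming a covariate.

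**The concern.** Standard treatment is written as a component of the assigned regimen, and assignment comes directly after the baseline score. On that reading, a patient coded Absent is scored untreated and then begins standard treatment and study drug together, so the change from baseline reflects two new treatments. A patient coded Present changes only study drug. Both kinds are pooled, and randomisation is not balanced on the variable that separates them, although it is known before allocation.

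Three things are at stake. Response in each arm would be partly due to standard treatment, so within-arm rates would be hard to interpret. The between-arm difference may be smaller than the 35 points on which the trial is sized. The arms could also differ by chance in their share of untreated patients.

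**Working it through.** **Inputs from protocol 5.9.** Response 64% (experimental) and 29% (control), z values 1.96 and 1.63, and 10% loss to follow-up.

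**The plan's own figure.** (0.64×0.36 + 0.29×0.71)/0.35² × (1.96 + 1.63)² = 45.9, so 46 per arm; 46 × 1.10 = 50.6, so 51. This reproduces. Exact enumeration of the two-sided 5% chi-square test with 46 per arm at 64% v 29% gives 92.8% power.

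**Assumed inputs (not in the document).** f is the share of patients untreated at baseline. r is the share of untreated placebo non-responders whom newly started standard treatment turns into responders.

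**Control arm, both models.** Rate = 0.29 + 0.71×r×f.

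**Model A: the same share r converts in both arms.** Experimental rate = 0.64 + 0.36×r×f, so the difference is 0.35×(1 − r×f).

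**Model B: constant shift on an underlying normal itch scale.** Among untreated patients the shift is s = Φ⁻¹(0.29 + 0.71r) − Φ⁻¹(0.29). The untreated experimental rate is Φ(Φ⁻¹(0.64) + s), and the arm's rate is the f-weighted average of this and 0.64.
- r = 0.2: control rate in the untreated 0.432; s = −0.171 + 0.553 = 0.382; experimental rate Φ(0.358 + 0.382) = 0.7705; with f = 0.5 the arm's rate is (0.64 + 0.7705)/2 = 0.705.
- r = 0.4: control rate in the untreated 0.574; s = 0.187 + 0.553 = 0.740; experimental rate Φ(1.098) = 0.864; with f = 0.5 the arm's rate is 0.752.

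**Power with 46 evaluable per arm (exact chi-square).**

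| f | r | Model A rates | Power | Model B rates | Power |
|---|---|---|---|---|---|
| 0 | – | 64.0% v 29.0% | 92.8% | same | 92.8% |
| 0.5 | 0.2 | 67.6% v 36.1% | 86.4% | 70.5% v 36.1% | 92.0% |
| 0.5 | 0.4 | 71.2% v 43.2% | 77.6% | 75.2% v 43.2% | 88.4% |
| 1 | 0.4 | 78.4% v 57.4% | 58.6% | 86.4% v 57.4% | 89.0% |

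The control rates agree across models. The power loss depends almost entirely on how standard treatment is assumed to act in the experimental arm.

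**Chance imbalance.** With 51 per arm and f = 0.5, treating the two counts as independent binomials, the chance that they differ by six or more is 27.6%. If one arm has three untreated patients above expectation and the other three below, Model A shifts the difference by (3/51)×r×(0.71 + 0.36): 1.3 points at r = 0.2 and 2.5 points at r = 0.4. The standard error of the difference is √[(0.64×0.36 + 0.29×0.71)/46] = 9.7 points.

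**The case against.** The strongest reply is that the key step is an inference. No sentence says that an untreated patient starts standard treatment at randomisation; the text could also mean that usual care is simply continued. This stands, and it is why the point is worded as a plain reading and asks for reconciliation. It does not remove the point, because a site cannot tell which meaning applies.

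A reader might go further and infer that the comparison is biased. The documents do not support that: standard treatment is in both arms, assignment is randomised and the trial is described as double-blind. Chance imbalance is already covered by the test's error rate, and its effect here is small against the standard error.

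A reader might also take the 58.6% power figure as the consequence. It needs every patient to be untreated, in which case no mixture exists, and it needs Model A; Model B gives 89.0% for the same f and r. Nor are large values of r clearly the protocol's own view. The Rationale says the usual agents often work poorly, although the Introduction mentions reports that gabapentin and pregabalin reduce itch. On mean WI-NRS change, which the Summary names as primary, a purely additive effect would leave the expected difference unchanged if the arms are balanced.

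Finally, covariates may be listed in a statistical analysis plan that is not shown, so their absence from 5.13 is not itself a fault. The stratification of the randomisation, however, is set in this protocol.

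**Conclusion.** The point holds in a limited form. The protocol lets patients with and without antipruritic treatment enter, assigns both to regimens that include it, and does not say whether it is continued or newly started relative to the baseline score. The consequence is heterogeneity, higher response in both arms and a possible dilution of the 35-point difference. The comparison between arms remains valid.

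The size cannot be fixed from the document. With half of patients untreated and r of 20-40%, power falls from 93% to somewhere between 92% and 78%, depending on r and on the model; f, r and the model are all assumptions. The case for stratifying therefore rests less on a large expected gain than on its very low cost. It is a worthwhile improvement, not a flaw that invalidates the trial.

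**What to change.** 1. Stratify the 1:1 block randomisation by baseline antipruritic use (Absent/Present), and include that factor in the week-6 comparisons of WI-NRS response and Skindex-10 change. The cost is a second randomisation list and one model term, with no extra patients or visits. The case record form already collects the information before allocation, but its field has only entries for antihistamine and others, so an explicit Absent/Present entry should be added.

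2. Reconcile 5.5 and 5.12 with 5.7 and 5.10 on whether standard symptomatic treatment means continued or newly started treatment relative to the baseline score. The cost is a clarifying sentence. Which clinical rule applies is for the investigators to decide.

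The first change deals with balance and heterogeneity but does not undo any dilution. Only the second shows whether dilution is in play, and so whether the 29% control rate suits this design.
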